6.1.6. Safety and Tolerability Measurements

Safety and tolerability evaluations will consist of AE reporting, clinical laboratory (hematology, biochemistry and urinalysis), IOP, ophthalmoscopy, and photography of affected cornea. Assessments will be performed in accordance with the schedule of assessments. Between clinical research centers, assessments will be standardized as much as possible.

Adverse Events

Recording of AEs will commence with signing of the ICF. AEs will be captured in the CRF. AEs will be followed up by the investigator as specified in Section 0, Adverse Event Reporting.

Clinical Laboratory Tests

Blood samples for serum chemistry and hematology and a mid-stream urine sample for urinalysis will be collected at the time points indicated in the schedule of assessments. The local clinical laboratory will clearly mark all laboratory test values that are outside the normal range and the investigator will indicate which of these deviations are clinically significant or not. The investigator must record all clinically significant abnormal values during the study in the AE section of the CRF.

Clinical significance is defined as any variation in signs, symptoms, or testing that has medical relevance according to the investigator and may result in an alteration in medical care.

The following tests will be performed:

• Hematology: full blood count (total red blood cell count / white blood cell count with differential), hematocrit, hemoglobin, platelets.

- Blood biochemistry: serum creatinine, aspartate aminotransferase, alanine aminotransferase, glucose, serum electrolytes (sodium, potassium), total protein, total bilirubin, alkaline phosphatase, gamma-glutamyl transferase, cholesterol and triglycerides.
- Urinalysis (by dipstick): specific gravity, pH, protein, glucose, ketones, urobilinogen, blood (erythrocytes, leucocytes).
- Pregnancy testing in urine (by dipstick) (for women of childbearing potential only).

Intraocular Pressure

At each visit, IOP measurement will be done using any CE marked tonometer (e.g., Goldmann, Icare or non-contact tonometers). For consistency, subjects should preferably be tested using the same equipment at each visit.

Ophthalmoscopy

Ophthalmoscopy will be performed after pupil dilatation to examine the vitreous, retina, macula and choroid at screening and at the final visit AND at any time if the vision deteriorates or either the pupil tests or IOP are abnormal.

6.2. Appropriateness of Measurements

The assessments which will be performed in this study are standard, and generally recognized as reliable, accurate and relevant.

6.2.1. Timing of Assessments

The date of all assessments will be recorded in the CRF.

When multiple assessments are scheduled at the same time, completion of questionnaires by the subject will be done before ocular assessments to be performed by the investigator.

6.3. Primary Efficacy Variables

The primary efficacy variable chosen to assess drug efficacy is the CRR_12 (the clinical resolution rate at 12 months from randomization, defined as the percentage of subjects cured 30 days after discontinuing all study therapies, within 12 months of randomization).

Criteria for clinical resolution:

A subject will be considered cured if resolution of all the following clinical signs are observed, resulting from a slit lamp examination:

- No corneal inflammation (including subepithelial infiltrates, stromal infiltrates and oedema) that requires treatment, with a healed corneal epithelium and minimal punctate staining (10 dots or less equivalent to Grade 1 on the Oxford Scale).
- No or mild conjunctival inflammation (including bulbar injection, bulbar oedema, tarsal hyperemia): mild conjunctival inflammation is acceptable if related to other concurrent conditions such as blepharitis.
- No limbitis, scleritis or anterior chamber inflammation.

6.4. Secondary Variables

The secondary efficacy variables are:

- BCVA
- Corneal scarring as identified by slit lamp examination
- Ulceration severity as identified by slit lamp examination using a 2 grade scoring procedure; i.e. present or absent
- Anterior chamber inflammation as identified by ophthalmoscopy using a 3 grade scoring procedure
- EQ-5D questionnaire
- VFQ25 questionnaire

The secondary safety variables are:

- Adverse events
- Clinical laboratory tests
- Intraocular pressure (IOP)
- Ophthalmoscopy
- Worsening of the corneal epithelial defect and definable inflammatory signs (development of ring abscess and hypopyon) despite >30 days of treatment with the study drug)
- Rate of subjects with a relapse
- Rate of subjects requiring surgery, including amniotic membrane transplants, superficial keratectomy, application of cyanoacrylate glue, therapeutic penetrating, lamellar keratoplasty, cataract surgery, evisceration, or enucleation
- Rate of subjects requiring non-study therapies, e.g., topical steroids and NSAIDs
- Rate of subject discontinuation from study: to permit alteration of anti-amoebic therapy or for other unrelated specified reasons.
- Incidence of secondary complications, such as significant corneal neovascularization, corneal scarring, corneal perforation, scleritis, secondary glaucoma, cataract, retinopathy.

7. STATISTICAL METHODS

All statistical analyses will be performed using the STATA or SAS® System, latest version available.

7.1. Study Analysis Sets

7.1.1. Analysis Data Sets for the Efficacy Analyses

Full Analysis Set (FAS)

All subjects who have been randomized and for whom the primary efficacy variable is assessed will be included in the FAS. The FAS will be used in all efficacy analyses.

Per-Protocol Analysis Set (PPAS)

All subjects in the FAS without any relevant protocol deviations. The criteria for inclusion in the PPAS will be described in the SAP and documented before code breaking. The PPAS will be used in the analysis of the primary efficacy variable only.

7.1.2. Analysis Data Set for the Safety Analysis

Safety Analysis Set

All subjects who have received at least 1 dose of study medication will be included in the Safety Analysis Set. This set will be used in all analyses of safety data.

7.2. Statistical Analytical Plan (SAP) for Efficacy, Safety and Tolerability Evaluation

A SAP with more technical and detailed elaboration of the principal features of the proposed statistical analyses, presentations, and the way in which anticipated analysis problems will be handled, will be written before the code is broken.

7.3. Demographic Variables and Baseline Characteristics

Demographic variables and baseline characteristics will be summarized in tabular form showing absolute and relative frequencies for categorical variables, and mean, standard deviation, median, 25th and 75th percentiles, minimum and maximum for continuous variables.

7.4. Evaluation of Efficacy Parameters

All efficacy evaluations will be based on the FAS. Moreover, the primary efficacy variable, CRR, will be evaluated also for the PPAS.

7.4.1. Primary Efficacy Variable

Since it is also possible to test for non-inferiority if the superiority hypothesis is not met, additional conditions are specified (see list below) to meet the strict requirements of a non-inferiority study, making it feasible to test for non-inferiority using the results from the superiority analysis, without a further separate analysis. The 90% confidence interval for the difference between the treatments

obtained from the superiority analysis gives the necessary information. Position of the lower end of the confidence interval relative to a pre-defined agreed 0.20 non-inferiority margin (Δ) provides the key information for making decisions (conclusions) about non-inferiority.

The additional conditions specified to make testing for non-inferiority feasible are the following:

- Pre-defined non-inferiority margin (Δ =0.20) based on both clinical and statistical considerations, i.e., chosen on the basis of external information and not chosen to fit the data.
- Analysis of the FAS and the PPAS, giving similar results with respect to p-values and confidence intervals for the efficacy measure at issue.
- Study design and implementation directed at minimizing deviation from protocol (a particularly important source of bias in non-inferiority studies), e.g., special care to minimize violations of: entry criteria; non-compliance; withdrawals; loss; missing data; etc. This should help ensure the second bullet point.
- Evidence that the standard treatment is showing its usual (expected) level of efficacy.

These specifications are in accord with the recommendations by the Committee for Proprietary Medicinal Products (CPMP) 482/99.

Null hypothesis superiority:

• No difference between test treatment and reference treatment

Non-inferiority clinical studies aim to demonstrate that the test treatment is no worse than the reference by more than a pre-specified small amount.

Null hypothesis non-inferiority:

• Test treatment is inferior to the reference by Δ or more

CRR_12 will be analyzed with a logistic regression model and model-based estimates of the difference between treatments, odds ratio with corresponding confidence intervals and p-values will be provided. Time-to-event (clinical resolution) analysis will also be performed for the comparison of CRR_12s between treatments, including the Cox Proportional Hazards regression (subject to validity of the 'proportional hazards' assumption) and Kaplan-Meier survival plots. If the proportional hazard assumption is not fulfilled a logrank test will be performed.

7.4.1.1. Justification for choice of the non-inferiority margin Δ

7.4.1.1.1. Justification on Statistical grounds

Our pre-defined non-inferiority margin of Δ =0.20 is based on previous studies (historical data), i.e., the study referred to in the protocol showing 1/20 cured without treatment being the only data available that can be used to estimate the cure with placebo, and the results of the reference (standard) treatment from the SIFI / Moorfields observational studies²⁰, adjusted for inclusion of

advanced disease cases in the study. The table below demonstrates the statistical grounds for the choice of Δ . The chosen Δ of 0.20 satisfies the condition that "the test treatment is expected to retain at least 50% of the standard treatment effect over placebo, in order to be considered as non-inferior".

Table 1 Selection of Non-Inferiority Margin (Δ) based on statistical issues

		Proportion
A	Cured with no treatment: Historic Data	0.05
В	Cured with Standard Treatment: SIFI Study Data	0.67
Ba	B adjusted for inclusion of stage-3 cases (63/100)	0.63
Ba(lower)	Lower 95% confidence interval (CI) bound for Ba (Binomial	
, ,	exact)	0.53
M1	Ba(lower) - A: the standard treatment effect over placebo	0.48
Δ	Non-inferiority Margin	0.20
roportion of	M1 retained by the Test Treatment: (M1 - Delta) / M1	58%
-	ment retains well over 50% of the Standard treatment effect o	-

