7.9.2 Justification for choice of the non-inferiority margin

On statistical grounds:

Our pre-defined non-inferiority margin of Δ =0.20 is based on previous studies (historical data), i.e., the study referred to in the protocol showing 1/20 cured without treatment being the only data available that can be used to estimate the cure with placebo, and the results of the reference (standard) treatment from the SIFI / Moorfields observational studies, adjusted for inclusion of advanced disease cases in the study. The table below demonstrates the statistical grounds for the choice of Δ . The chosen Δ of 0.20 satisfies the condition that "the test treatment is expected to retain at least 50% of the standard treatment effect over placebo, in order to be considered as noninferior".

Table 1: Selection of Non-Inferiority Margin (Δ) based on statistical issues

		Proportion	
Α	Cured with no treatment: Historic Data	0.05	
В	Cured with Standard Treatment: SIFI Study Data	0.67	
Ва	B adjusted for inclusion of stage-3 cases (63/100)	0.63	
Ba (lower)	Lower 95% CI bound for Ba (Binomial exact)	0.53	
M1	${f Ba}$ (lower) – ${f A}$: the standard treatment effect over placebo	0.48	
Δ	Non-inferiority margin	0.20	
Proportion of M1 retained by the Test treatment; $(M1 - \Delta)/M1$ 58%			
The Test Treatment retains well over 50% or the Standard treatment effect over placebo			

On clinical grounds:

The Sponsor proposes as clinically acceptable a non-inferiority margin of 0.20: this is within the accepted level for a study of this kind in view of the following:

- A poor response to therapy is common in this disease. Disease progression is slow in this disease (over weeks and months) and clinicians have to assess the effect of treatments every 1-2 weeks, in cases not progressing well, and modify therapies to optimize outcomes. Because of the disease chronicity the use of an ineffective treatment for these periods results in a delayed response, but no serious short term morbidity. The study results may indicate non-inferiority, when at worst the true difference in proportion 'cured' (Combined PHMB alone) is 0.20. The most likely impact of such a finding on clinical practice will be to encourage the use of PHMB monotherapy as a first line treatment.
- However, if PHMB monotherapy fails in clinical practice during the early stages of treatment, which is
 to be expected in some subjects, the clinician is unlikely to abandon the good clinical practice of

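### Table 1 gives the treated rate a 95% bound but enters the untreated rate (1 of 20) as a fixed 0.05, so the stated retention of more than half the standard effect is not supported at the table's own confidence level

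*Protocol*

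**What the plan says.** Protocol 7.4.1.1.1 and SAP 7.9.2 justify the margin of 0.20 with the same Table 1. The standard-treatment rate is 0.67, adjusted to 0.63 for late-stage cases and treated as 63/100. Its exact lower 95% bound is given as 0.53. The untreated rate comes from a historical series "showing 1/20 cured without treatment being the only data available that can be used to estimate the cure with placebo" and enters as 0.05. M1 is defined as "Ba(lower) - A: the standard treatment effect over placebo", giving 0.48. Retention is (M1 - Δ)/M1, stated as 58%.

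Two conclusions follow. The Protocol sets as its criterion that "the test treatment is expected to retain at least 50% of the standard treatment effect over placebo", and says that a margin of 0.20 meets it. The SAP table ends: "The Test Treatment retains well over 50% or the Standard treatment effect over placebo"; the Protocol table ends with the same statement.

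Neither document gives a confidence limit for 1/20, carries its error into M1, or varies it in a sensitivity analysis. Protocol 7.4.1 and SAP 7.9.1 make a margin with both clinical and statistical grounds one of the conditions for testing non-inferiority.

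**The concern.** Table 1 allows for sampling error in one of its two historical rates and not in the other. The rate left as a constant comes from the smaller sample (20 against 100) and carries the larger one-sided error. The exact upper limit for 1/20 lies 0.199 above its estimate (0.249 - 0.05). The exact lower limit for 63/100 lies 0.102 below its estimate (0.63 - 0.528).

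The label on M1 and the 95% bound inside it lead a reader to take 0.48 as a conservative estimate of the effect over placebo. It is conservative in one component only. At stake is a stated property of the threshold that decides non-inferiority: whether 0.20 keeps at least half of the standard effect. A regulator can recompute this from the table alone.

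**Working it through.** **Inputs.** From Table 1 in both documents: treated 63/100, untreated 1/20, two-sided 95% level, Δ = 0.20, retention = (M1 - Δ)/M1, criterion at least 50%. Assumption: 63/100 is a real count, as the table treats it.

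**The plan's figure.** The exact lower 95% bound for 63/100 is 0.528. M1 = 0.528 - 0.05 = 0.478, and (0.478 - 0.20)/0.478 = 58%. Table 1 reproduces.

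**What 50% retention needs.** (M1 - 0.20)/M1 ≥ 0.50 requires M1 ≥ 0.40. With the treated bound held at 0.528, the untreated rate must be at most 0.528 - 0.40 = 0.128 (0.13 from the rounded 0.53). If the true untreated rate were 0.13, none or one of 20 would be cured about 25% of the time, so 1/20 does not exclude it.

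**Both errors included.** M1 is taken as the lower 95% limit of 63/100 minus 1/20 (point difference 0.58). For Newcombe, the Wilson lower limit for 63/100 is 0.532 and the Wilson upper limit for 1/20 is 0.236:

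M1 = 0.58 - √[(0.63 - 0.532)² + (0.236 - 0.05)²] = 0.58 - 0.210 = 0.370; retention = (0.370 - 0.20)/0.370 = 46%.

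| 95% method | M1 | Retention |
|---|---|---|
| Square-and-add, Jeffreys limits (0.533; 0.211) | 0.392 | 49% |
| Agresti-Caffo | 0.384 | 48% |
| Miettinen-Nurminen | 0.377 | 47% |
| Newcombe | 0.370 | 46% |
| Square-and-add, exact limits (0.528; 0.249) | 0.356 | 44% |
| Exact lower minus exact upper (0.528 - 0.249) | 0.279 | 28% |
| Wald | 0.446 | 55% |
| Wald, continuity-corrected | 0.416 | 52% |

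The stacked exact bounds are deliberately conservative. Wald is unreliable with one event in 20.

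**At 90% instead of 95%.** Agresti-Caffo gives 51%, Newcombe 52%, Miettinen-Nurminen 52% and Wald 57%. Square-and-add of exact limits gives 49%.

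**Sensitivity to the untreated rate,** using the plan's formula with 0.53 held fixed:

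| Untreated rate | M1 | Retention |
|---|---|---|
| 0.05 | 0.48 | 58% |
| 0.10 | 0.43 | 53% |
| 0.13 | 0.40 | 50% |
| 0.15 | 0.38 | 47% |
| 0.20 | 0.33 | 39% |

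The 0.15 row is not remote. Protocol 1.2 describes the 1 in 20 as a good outcome and, in the same sentence, reports 3 medical cures. Whether 3/20 is the relevant untreated rate is an assumption that the documents do not settle.

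**The case against.** **The table has no arithmetic error.** This stands. Every cell reproduces. The fault lies in how M1 is constructed, and neither document says in words that M1 must be a lower bound on the difference. On point estimates alone, retention would be (0.58 - 0.20)/0.58 = 66%. But the table itself chose a 95% bound for the treated rate, and gives no reason for treating the less certain rate as known.

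**The failure depends on method and level.** This also stands. The trial's main inference uses a 90% interval, and at 90% most methods give slightly more than half. The 95% level is used here because Table 1 uses it. Even the 90% small-sample results, at 51% to 52%, do not support a claim of comfortable retention.

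**A reader might infer that a trial result just inside -0.20 would not show that most of the standard effect is kept.** The documents do not support that. Non-inferiority is judged on the lower confidence limit. Take 58 per arm (116 evaluable, SAP 5.1) and, as an assumption, rates near 0.63 in both arms:

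- SE = √(2 × 0.63 × 0.37/58) = 0.0897. A 90% lower limit at -0.20 means an observed difference of -0.20 + 1.645 × 0.0897 = -0.053.
- Testing 50% retention directly, with the error of both historical rates: z = (-0.053 + 0.5 × 0.58)/√[0.0897² + 0.25 × (0.63 × 0.37/100 + 0.05 × 0.95/20)] = 0.237/0.096 = 2.47, one-sided p = 0.007.
- With the standard error of 1/20 widened to (0.249 - 0.05)/1.96 = 0.101, z = 2.24 and p = 0.012.

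So, if the historical effect carries over to this trial (which Table 1 also needs), such a result would support retention above one half. The shortfall arises when a margin is set against a worst-case M1.

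**The inputs are weak for any precise figure.** This stands. 63/100 is an adjusted rate, not shown to be an observed sample, and the two series are unrelated, so sampling error is not the only uncertainty. No replacement percentage should be called assured.

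**Conclusion.** The point holds as a methodological error in the margin's justification. M1 = 0.48 is not a 95% lower bound on the effect over placebo. At the table's own level, and taking 63/100 and 1/20 as real counts, small-count methods put M1 at about 0.36 to 0.39. Half of that is about 0.18 to 0.20, just under the 0.20 margin, and retention is about 44% to 49%. The statements that the 50% condition is satisfied, and by a good distance, are therefore unsupported.

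The shortfall is modest, at 1 to 6 percentage points below one half except with stacked exact bounds, and it is not universal across methods and levels. A reader might go further and infer that 0.20 is the wrong margin or that the test is invalid. The documents do not support that: the margin also has a separate clinical justification (Protocol 7.4.1.1.2; SAP 7.9.2), and nothing here alters the test or the sample size.

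**What to change.** In Protocol Table 1 and SAP Table 1:

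- Define M1 as the lower 95% confidence limit of the difference 63/100 minus 1/20, by a named method. With Newcombe, M1 is 0.37 and retention 46%.
- Show the range over methods and over plausible untreated rates, noting that the plan's own formula reaches 50% at an untreated rate of about 0.13.
- Delete the closing line of each table and the sentence saying that the 50% condition is satisfied.
- State that statistical retention is about one half and uncertain, so the margin rests mainly on the clinical argument. Do not describe any percentage as assured.

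Keep Δ = 0.20, the test and the sample size. The work is one recalculated row, a short sensitivity display and some wording in two documents. The downside is a less favourable stated retention figure.

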7.4.1.1.2. Justification on Clinical grounds

The Sponsor proposes as clinically acceptable a non-inferiority margin of 0.20: this is within the accepted level for a study of this kind in view of the following:

- A poor response to therapy is common in this disease. Disease progression is slow in this disease (over weeks and months) and clinicians have to assess the effect of treatments every 1-2 weeks, in cases not progressing well, and modify therapies to optimize outcomes. Because of the disease chronicity the use of an ineffective treatment for these periods results in a delayed response, but no serious short term morbidity. The study results may indicate non-inferiority, when at worst the true difference in proportion 'cured' (Combined PHMB alone) is 0.20. The most likely impact of such a finding on clinical practice will be to encourage the use of PHMB monotherapy as a first line treatment.
- However, if PHMB monotherapy fails in clinical practice during the early stages of treatment, which is to be expected in some subjects, the clinician is unlikely to abandon the good clinical practice of monitoring the disease progress closely, and adding other antiamoebics to the therapy when necessary.
- At worst, the impact of the study finding might result in a little delay (matter of days) in starting a combined treatment in some patients, whilst giving a chance for the biguanide mono-therapy to act. This scenario is unlikely to result in blindness or serious morbidity. It may cause some delay in the clinical resolution.

• By contrast, the possibility that the true difference may be much smaller than 0.2, or even in favor of PHMB mono-therapy, will have important beneficial consequences for patients and ophthalmic services.

7.4.2. Secondary Efficacy Variable

Which test to be used in the analyses of secondary efficacy variables depends on the type of variable, e.g., logistic regression for binary variables, proportional odds model for an ordinary scaled variable, analysis of variance (ANOVA) or covariance (ANCOVA) for continuous variables as appropriate. If the underlying assumptions are not fulfilled, data transformation or non-parametric test will be performed. For comparison of proportions, Chi square tests, Fisher's exact test, or Mantel-Haenszel procedures, as appropriate, will be considered. For continuous variables, the Wilcoxon rank-sum test or rank ANOVA/ANCOVA will be used. The STATA or SAS statistical software will be used for the analysis.

EQ-5D and VFQ25 will be evaluated according to their respective analysis protocols.

